7 STUDY SELECTION CRITERIA

7.1 INCLUSION CRITERIA

At least one eye of each participating subject should meet inclusion criteria.

1. Male or female subjects, 22 years or older.
2. Visually significant cataract.
3. Diagnosed with mild to moderate open angle glaucoma (e.g. primary open angle glaucoma, pigmentary glaucoma, pseudoexfoliative glaucoma) as documented in subjects' medical record substantiated using funduscopic exam or OCT and at least one visual field test using the SITA Standard 24-2 testing algorithm.
O [REDACTED]
I [REDACTED]
I [REDACTED]
I [REDACTED]
4. At screening, [REDACTED] on 1-5 IOP-lowering medications (For combination IOP-lowering medications that consist of two or more IOP-lowering drugs, each IOP-lowering drug component counts as a separate medication.) with a stable medication regimen for at least two months prior to screening visit.

5. At baseline, [REDACTED] IOP at least 3 mmHg higher than screening IOP.
6. Scheduled for cataract extraction followed by either:
 - a) ab-interno transluminal viscoelastic delivery with trabeculotomy using OMNI surgical System
 - d) ab-interno transluminal viscoelastic delivery using OMNI surgical System
 - e) [REDACTED]
7. Shaffer grade of \geq III in all four quadrants.
8. Potential of good best corrected visual acuity post cataract extraction, in the investigator's judgment
9. Able and willing to comply with the protocol, including all follow-up visits.
10. Understand and sign the informed consent.

7.2 EXCLUSION CRITERIA

A subject who meets any of the exclusion criteria listed below will not receive the study procedure:

1. Any of the following prior treatments for glaucoma:
 - o Laser trabeculoplasty \leq 3 months prior to baseline
 - o Implanted with iStent (All types), Cypass, Xen, Express, glaucoma draining device/valve, or Hydrus Device
 - o Prior canaloplasty, goniotomy, trabeculotomy, trabeculectomy, ECP or CPC
2. Acute angle closure, normal tension, traumatic, congenital, malignant, uveitic, neovascular or severe glaucoma as documented in subjects' medical record.
3. Concurrent IOP-lowering procedure other than one of the study procedures listed under inclusion criterion 6 at the time of cataract surgery (e.g. ECP, CPC, etc.)
4. In the Investigator's judgement, predisposed to significant risk because of washout of ocular hypotensive medications.
5. Concurrent ocular pathology or systemic medical condition which, in the Investigator's judgment, would either place the subject at increased risk of complications, contraindicate surgery, place the subject at risk of significant vision loss during the study period (e.g., wet AMD, corneal edema, Fuch's dystrophy, active intraocular infection or inflammation within 30 days prior to Screening Visit, etc.), or interfere with compliance to elements of the study protocol (e.g., returning to Investigator's office for follow-up visits).
6. History of penetrating keratoplasty or another corneal transplant; corneal abnormality that would prevent reliable IOP measurement; e.g. keratoconus or abnormally thick or thin cornea.
7. BCVA of logMAR 1.0 (20/200) or worse in the fellow eye not due to cataract.
8. Participation (\leq 30 days prior to baseline) in an interventional trial which could have a potential effect on the study outcome, as determined by the study investigator.
9. Women of childbearing potential if they are currently pregnant or intend to become pregnant during the study period; are breast-feeding; or are not in agreement to use adequate birth control methods to prevent pregnancy throughout the study.

8 STUDY PROCEDURES

8.1 STUDY SCHEDULE

8.2 NUMBER OF SUBJECTS, DURATION OF FOLLOW-UP AND STUDY DURATION

Approximately 459 subjects will be randomized (1:1:1) to treatment, [REDACTED]
[REDACTED] No site
will randomize more than 25% of the total number of subjects without prior approval
from Sponsor.

[REDACTED]

Study subject participation will be from approximately 35 months, (at a minimum) to 40 months, depending on the length of the required medication washout prior to baseline and if additional washout is needed [REDACTED] for subjects presenting at these visits with ocular hypotensive medication.

It is anticipated that the enrollment period for the study will last approximately 24 months. Including the 40-month follow-up period, the study is expected to last 54 months.

8.3 INFORMED CONSENT AND POINT OF ENROLLMENT

The IRB-approved informed consent will be presented and explained to each prospective subject by the investigator or a trained clinical professional. Once the subject has had ample time to read the consent form, has been informed of all aspects of the study, and has had an opportunity to ask questions, the subject will be given a choice to voluntarily confirm his or her participation in the study as documented by completion of the Informed Consent. After signing the Informed Consent and the HIPAA (Health Insurance Portability and Accountability Act) authorization, the subject can then proceed with the screening visit. The subject has the right to withdraw from the study at any time without consequences, as indicated in the Informed Consent Document.

The subject's signed and dated informed consent must be obtained before conducting any study specific procedures that are not part of the standard of care. Subjects are enrolled upon signing the ICD even if they subsequently fail to meet the eligibility criteria.

The principal investigator(s) must retain the original, signed written Informed Consent Document. A copy of the written Informed Consent Document must be given to the subject.

8.4 SCREENING VISIT

After obtaining an understanding of the purpose of this study, then reviewing and signing the Informed Consent Document, all potential subjects will undergo an initial screening examination in order to determine their eligibility for the study. Exams and tests listed in the Screening column of Table 1 should be performed. Refer to Appendix A for instructions for performing the exams.

Exam data collected on subjects prior to enrollment as part of the routine clinical practice may serve as Screening data as long as it was collected within 15 days prior to the visit. The only exceptions to this are:

- IOP and IOP-lowering medications. These data must be collected at the Screening visit.
- Visual field: Visual Fields conducted per the protocol method (Humphrey 24-2 SITA standard) within 6 months of the screening visit will be acceptable.

8.5 WASHOUT OF HYPOTENSIVE MEDICATIONS

Subjects on ocular hypotensive medication who meet all eligibility criteria at the screening visit will be instructed to discontinue their ocular hypotensive medication regimen, and to return for a Baseline visit after completing the appropriate washout period. The final eligibility assessment will happen at baseline visit.

If the study subject fails to remember to not use ocular hypotensive medication for the study eye per the required washout period, they can be re instructed to restart washout and return for the Baseline or other washout IOP visits as long as it falls within the specified visit window. If deemed necessary by the PI, a subject can be given hypotensive medications after the baseline visit until the day of surgery. An oral hypotensive medication can be used between baseline to surgery. The minimum washout periods are specified in Table 2 below.

This figure is a 2D bar chart representing a 3x10 grid of data. The data is organized into 10 horizontal rows. Each row contains three bars: a black bar on the left, a white bar in the middle, and a black bar on the right. The height of each bar corresponds to a value in the grid. The first column of bars is the tallest, indicating the highest values in the first column of the grid. The last column of bars is the shortest, indicating the lowest values in the last column of the grid. The middle column of bars has the highest height in every row, suggesting a central peak or a specific feature in the data.

8.6 BASELINE VISIT

After appropriate washout during the Baseline visit, the exams and tests listed in the Baseline column of Table 1 should be performed in order to determine final eligibility for the study. If both eyes meet the applicable inclusion and exclusion criteria, the eye with higher IOP will be included in the study. In case of both eyes with same IOP at baseline,

investigator will select the study eye. Subjects meeting all criteria at the Baseline Visit will be scheduled for surgery and be randomized to a treatment arm. Randomization to treatment group will be performed using a 1:1:1 ratio and will be stratified by site. Computer-generated randomization will be administered through the electronic data capture (EDC) system with separate randomization sequences for each clinical site.

Refer to Appendix A for instructions for performing the exams.

8.7 SURGICAL PROCEDURE

Only eyes with uneventful cataract extraction will receive one of the following surgical procedures based on randomization:

1. Ab-interno transluminal viscoelastic delivery (up to 360 degrees) and trabeculotomy (at least 180 degrees and up to 360 degrees) using the OMNI Surgical System
2. Ab-interno transluminal viscoelastic delivery (up to 360 degrees) using the OMNI Surgical System
3. [REDACTED]

Eyes with complications related to previous glaucoma interventions or cataract extraction (such as posterior capsular rent or vitreous presentation) should be exited from the study. The region where the trabeculotomy procedure is performed (e.g. superior hemisphere) and the extent of trabeculotomy should be recorded on the case report forms.

[REDACTED]

[REDACTED]

Surgeons should follow their standard intra-operative and peri-operative medication regimen.

8.8 FOLLOW-UP VISITS

Follow-up visits should be performed according to the schedule provided in Table 1. All attempts should be made to conduct each follow-up visit within the time interval specified in Table 1. Evaluations conducted outside the prescribed time period will be considered protocol deviations.

NOTE: A safety IOP check anytime between the predefined visits (especially where the visits are sparse such as between 6 and 12 months) may be performed at the Investigator's discretion where warranted to ensure subject safety.

8.9 UNSCHEDULED VISITS

An unscheduled visit will be any visit to the clinical site, other than those specified in the protocol, at which the subject has a complaint regarding the study eye and/or treatment to the study eye is required or changed. The Investigator and/or qualified investigational staff will perform the procedures necessary to evaluate the study participant at these visits and will record the visit in the subject's medical records and on the CRF. No specific testing is required.

8.10 MANAGEMENT OF IOP AFTER SURGERY

In general, the primary consideration for the reintroduction of hypotensive medication is the preservation of the retinal nerve fiber layer, optic nerve and visual field.

[REDACTED] Administration of glaucoma medication in subjects with IOP < 21 mmHg will be considered on a case-by-case basis by the study Investigator and the sponsor.

No more than one ocular hypotensive agent should be added at a single visit or within a 2-week period, without prior approval of the sponsor.

In the event of a steroid response increase in IOP due to prolonged anti-inflammatory regimen, the guidelines above to treat increase in IOP should be followed; however, topical hypotensive medications should be discontinued once the topical steroid has been discontinued.

Since the study population is undergoing angle surgery involving use of an ophthalmic viscoelastic agent, which is known to cause IOP spikes in some patients in the immediate postoperative period, use of glaucoma medications in the first month after surgery will be allowed at the discretion of the study Investigator. This short-term use of glaucoma medications in the immediate postoperative period will not be considered "rescue therapy" and will not be considered in the effectiveness analyses for the study.

For subject safety, a change in medical therapy may be implemented or additional surgical measures may be performed at any time during the study at the Investigator's discretion in the event it is required. The primary concern of the Investigator and

Sponsor at all times is the health and safety of the subjects. Usage of hypotensive medications specifically indicated for prevention of IOP spikes following Nd:YAG capsulotomy and administered for up to 72 hours after Nd:YAG capsulotomy will not be considered rescue therapy.

Medications which have been re-started by the Investigator may be discontinued if the Investigator's judgment is that the target intraocular pressure has been reached and the continued use of some or all of the therapy may not be required. Discontinuation of medications after re-introduction is recommended to be in the reverse order of re-introduction. The rationale for discontinuation should also be documented in the subject's medical record.

A record of all ocular hypotensive medications added, discontinued or changed will be documented on the appropriate CRF for each scheduled visit or on a CRF for an Unscheduled Visit, if necessary.

Another potential reason for intervention is hypotony. Intervention should only be considered if the hypotony has caused or is likely to cause sequelae such as a flat chamber or retinal detachment. No intervention is indicated when the vision is unchanged from screening, there is no persistent choroidal detachment, the anterior chamber is not flat with lens corneal touch, or the patient is asymptomatic. No intervention should be undertaken for hypotony which is not causing, or threatening to cause, a reduction in vision.

Secondary IOP-Lowering Interventions to Control IOP

If the subject requires another glaucoma procedure to control their IOP, the subject should continue to be followed according to standard of care until the adverse event resolves or 1-month post-re-intervention, whichever is longer. Following this, the subject should be withdrawn from the study.

Subjects who have had a secondary IOP-lowering intervention will be considered treatment failures for the purpose of the endpoint analyses. For the primary effectiveness endpoint of the study, the corresponding baseline unmedicated DIOP will be used to impute the 12-month unmedicated DIOP. These subjects will be included in the Safety Endpoint analyses through their withdrawal from the study.

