10.4.1 PRIMARY EFFECTIVENESS ENDPOINT

The primary analysis of the primary effectiveness endpoint will be based on the AT population. The Baseline unmedicated DIOP will be used to impute the 12-month unmedicated DIOP for the subjects meeting any of the following criteria:

- Ocular hypotensive medications cannot be washed out properly at 12 months due to safety reasons.
- Have secondary surgical interventions (such as laser procedure or MIGS) to control IOP before the 12-month washout.
- Have any ocular procedures that can affect the IOP before the 12-month washout.

- Have IOP below 6 mmHg at 1 month or later
- Do not have the 12-month washed out DIOP due to any other reasons.

The change in unmedicated DIOP from baseline at 12 months will be calculated for each study eye as change = (12-month unmedicated DIOP – Baseline unmedicated DIOP).

The descriptive statistics (such as mean, standard deviation, median, minimum, and maximum) of the medication-free mean diurnal IOP and the change from baseline and the 95% confidence interval of the mean will be calculated for each of the three study groups. A two-sample t-test with a one-sided significance level of 0.025 will be used to compare the mean unmedicated DIOP change from baseline at 12 months for Hypotheses I and II described in Section [10.1](#). The two-sided 95% confidence interval based on the t-distribution will also be provided for the mean difference. In order to assess the pattern of the distribution, box-plots will be prepared for the medication-free mean diurnal IOP and its change from baseline for each of the three study groups.

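### In section 8.10 the four no-intervention conditions for hypotony are joined by *or*, so read literally any one suffices, which clashes in practice with the sentences before and after it

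*Combined protocol and SAP*

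**What the plan says.** Section 8.10 of the combined protocol and SAP turns to low pressure with the words "Another potential reason for intervention is hypotony". Three sentences follow, labelled A, B and C here.

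- **A:** "Intervention should only be considered if the hypotony has caused or is likely to cause sequelae such as a flat chamber or retinal detachment".
- **B:** "No intervention is indicated when the vision is unchanged from screening, there is no persistent choroidal detachment", continuing "the anterior chamber is not flat with lens corneal touch, or the patient is asymptomatic".
- **C:** "No intervention should be undertaken for hypotony which is not causing, or threatening to cause, a reduction in vision".

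Earlier in the same section there is a general safety clause, not specific to hypotony: "additional surgical measures may be performed at any time during the study at the Investigator's discretion in the event it is required".

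Section 10.4.1 sets a subject's 12-month unmedicated DIOP to the baseline value under any of five criteria. One is "Have any ocular procedures that can affect the IOP before the 12-month washout". Another, listed separately, is an IOP under 6 mmHg at 1 month or later.

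**The concern.** Sentence B is a list of reassuring findings closed by *or*. Taken at its word, each finding alone settles the matter. An eye with a flat chamber and no symptoms is then an example of what A says to consider and, at the same time, an eye for which B says nothing is indicated. B also cuts across the forward-looking wording on either side: A covers sequelae that are only likely, and C leaves open vision that is only threatened. The chamber finding is worded differently too, since A speaks of a flat chamber and B of flatness with lens-corneal contact.

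Hypotony is an anticipated event in this trial: a footnote to section 9.2 separates early from late forms. Up to 30 sites (section 5.2) will apply this paragraph. If some take B's conditions as alternatives and others take them jointly, the same clinical picture can be managed differently from site to site.

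**Working it through.** The plan gives no figure to reproduce here. The check has two parts: the logic of B against A and C, and the path from a hypotony procedure to the primary endpoint.

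**1. Inputs.** Code B's four conditions as yes/no: V (vision unchanged), D (no persistent choroidal detachment), F (chamber not flat with touch), S (asymptomatic). That gives 2⁴ = 16 combinations.

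**2. The two readings of B.**
- Alternative, as written (V or D or F or S): only the combination with all four answered *no* escapes, so B rules out 16 − 1 = 15.
- Joint (V and D and F and S): B rules out 1.
- The readings differ on 15 − 1 = 14 combinations.

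**3. Eyes with a flat chamber and touch (F = no).** There are 2³ = 8 combinations.
- Alternative: 8 − 1 = 7 ruled out. Joint: 0.
- If also asymptomatic (S = yes), 2² = 4 combinations. Alternative: all 4 ruled out. Joint: 0.

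**4. B set beside A and C.**

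| Eye | A | B, alternative | B, joint | C |
|---|---|---|---|---|
| Flat chamber with touch, asymptomatic | open for consideration | not indicated | not ruled out | turns on vision |
| Chamber not flat, sequelae judged likely | open for consideration | not indicated | ruled out only if the other three findings are also reassuring | turns on vision |
| Vision unchanged but threatened | turns on sequelae | not indicated | ruled out only if the other three findings are also reassuring | not barred |

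Under the alternative reading the one combination left open already has a flat chamber with touch and changed vision. The references to likely sequelae in A and to threatened vision in C then do no work. Under the joint reading the clash shrinks to the single combination with all four reassuring findings, where sequelae could still be judged likely or vision threatened.

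**5. Path to the primary endpoint (section 10.4.1).** An imputed eye has change = baseline − baseline = 0. With no other imputation criterion met:

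| IOP below 6 mmHg at 1 month or later | IOP-affecting procedure for hypotony before the 12-month washout | 12-month value used |
|---|---|---|
| Yes | Yes | baseline |
| Yes | No | baseline |
| No | Yes | baseline |
| No | No | observed |

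In the first two rows the decision to intervene changes nothing. It can matter only in the last two, for instance when hypotony is treated by a procedure and resolves within the first month. The documents as available give neither a hypotony rate nor a pressure cut-off for hypotony, so those eyes cannot be counted.

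**The case against.** Much of the other side's case is sound.

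- **There is no formal contradiction.** A is framed as a necessary condition and does not direct anyone to intervene. A, B and C can be applied cumulatively without logical inconsistency. This stands: a reader might infer that the protocol orders two opposite actions for one eye, and it does not. What remains is a conflict of practical guidance, because A tells sites which eyes to think about and B, read literally, removes nearly all of them.
- **B was probably meant jointly.** That is plausible, since the list gathers reassuring findings, and it would largely remove the clash. But the text does not say so, and the wording would then need correcting anyway.
- **The investigator can act regardless.** The safety clause in 8.10 allows this, so it cannot be assumed that a site would withhold needed treatment. The clause is general and does not say how A, B and C fit together.
- **The chamber wording is not a moving threshold.** In A the flat chamber is only an example of sequelae. This stands; uniform wording is a matter of tidiness.
- **The endpoint is mostly protected.** A reader might infer that sites reading B differently would produce different primary values. The separate criterion for IOP below 6 mmHg closes most of that route.
- **Safety reporting is protected as well.** Section 9 requires adverse events in the eye to be documented whatever their relation to the device, with any treatment recorded. Hypotony is therefore captured whether treated or not; at most, counts of secondary interventions could vary.

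**Conclusion.** The concern holds as a conflict of practical guidance in an operative safety rule. It rests on taking *or* at face value, which the text permits and nothing in it corrects. It bears on subject safety and on uniform conduct across sites.

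The 15, 1 and 14 out of 16 describe how far the two readings diverge in logic. The combinations are not shown to be equally likely or independent, so the counts say nothing about how many eyes are affected, about risk or about bias. An effect on the primary endpoint is possible only for eyes that have an IOP-affecting procedure for hypotony and never show IOP below 6 mmHg at 1 month or later; their number cannot be derived from the documents. Sample size, significance level and power are untouched.

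**What to change.** The sponsor's clinical lead should reconcile the three hypotony sentences in 8.10 into one consistent rule, so that a given eye gets one answer. The revised text should state whether the four conditions are joint or alternative, describe the chamber finding in one way throughout, and agree with the sentences on likely sequelae and threatened vision. The clinical content is for the sponsor to decide.

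The cost is one paragraph in a protocol amendment, IRB review as section 13 requires, and a memo to sites. No new data, procedures or analyses are needed.
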